9.4 STATISTICAL ANALYSES

9.4.1 GENERAL APPROACH

9.4.2 ANALYSIS OF THE PRIMARY EFFICACY ENDPOINT(S)

Our primary outcome, the proportion of women with complete IUD expulsion at 6 months after delivery in the two groups, will be compared in the modified intention-to-treat (MITT) cohort using the Wald test. Women who change their mind about receiving the IUD after randomization, choose to receive the IUD after 6 months, or women who choose not to participate in the study any time after randomization, will be excluded from analysis for the MITT analysis. In addition, we will present a per-protocol analysis. The per-protocol analysis will include women who received their treatment according to the timeframe in which they were randomized. For the early IUD insertion group, per-protocol analysis will include women with documented receipt of the IUD insertion between 14 and 28 days postpartum. For the interval IUD insertion group, the per-protocol analysis will include only women with documented receipt of a postpartum IUD between 42-56 days postpartum. In both the MITT and per-protocol analyses IUD expulsion rates will be compared using the 2-sided test of noninferiority. If the CI for the risk difference does not cross the prespecified 6% margin, noninferiority will be confirmed.

We will consider imputing missing data. However, if one group had no or few expulsion outcomes the model may not converge.

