4 STUDY DESIGN

4.1 OVERALL DESIGN

This is a multi-site, two-arm, non-blinded randomized controlled non-inferiority trial that includes 6 months of participation from enrollment to final follow-up.

Hypothesis: We hypothesize that the EPP IUD expulsion rate at 6 months postpartum will be lower than the reported expulsion rate for IPP IUDs (24%) and non-inferior at a 6% margin to the expulsion rate for interval postpartum IUDs (previously reported at 3-5%).

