9.2 SAMPLE SIZE DETERMINATION

We hypothesize that EPP IUD expulsion will be non-inferior to interval insertion. We propose that greater than or equal to a 6% difference in expulsion at 6 months postpartum between the two arms is clinically meaningful (6% non-inferiority margin). Therefore, we estimate that 404 women will be needed [202 in each arm] to achieve an 80% power to detect a difference of 6% in expulsion at 6 months at a significance level of .05 (two-sided alpha), assuming a 15% loss to follow up and that 5% of IUDs would not be placed after randomization (due to patient preference or new medical contraindication or inability to place the IUDs) and assuming a 4% expulsion rate in the interval group. We estimate that enrolling 404 patients allows us to achieve an 80% power to detect a difference of 6% or more between groups with a 1-sided type 1 error of 0.25%.

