9.4.3 ANALYSIS OF THE SECONDARY ENDPOINT(S)

Partial IUD expulsion and perforation will be analyzed with the same methods as the primary outcome. IUD discontinuation over the six-month study period will also be analyzed using survival analysis. Data will be censored either (1) at the last date of contact if a participant is lost to follow up or (2) time of IUD removal. The Log-rank test will be used for an unadjusted comparison of the two survival functions. This will be presented graphically using Kaplan-Meier curves.

For other secondary outcomes, normally distributed, continuous variables will be compared using Student's t-tests as appropriate. The Mann-Whitney U test will be used to compare other continuous variables that are not normally distributed. Proportions will be compared using chi-square tests. For small cell sizes, Fisher's exact test will be used as appropriate.

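### The primary non-inferiority rule rests on a Wald test with no stated confidence level; read as a 95% Wald interval, it falsely declares non-inferiority in 3.0-3.6% of trials, not 2.5%

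*Combined protocol and SAP*

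**What the plan says.** Section 9.4.2 states that the primary outcome, complete IUD expulsion at 6 months, "will be compared in the modified intention-to-treat (MITT) cohort using the Wald test". It continues: "In both the MITT and per-protocol analyses IUD expulsion rates will be compared using the 2-sided test of noninferiority". The decision rule is: "If the CI for the risk difference does not cross the prespecified 6% margin, noninferiority will be confirmed". The section does not say how the interval is built or at what level, and the general-approach section before it (9.4.1) is a heading with no text.

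Section 9.2 gives two error rates. One sentence plans "at a significance level of .05 (two-sided alpha"); the next claims 80% power "with a 1-sided type 1 error of 0.25" percent. Attrition is planned "assuming a 15% loss to follow up and that 5% of IUDs would not be placed after randomization". The assumed interval-arm rate is 4%, and section 4.1 gives the background as "the expulsion rate for interval postpartum IUDs (previously reported at 3-5" percent.

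Section 9.4.3 carries the method further: "Partial IUD expulsion and perforation will be analyzed with the same methods as the primary outcome". Its provision for Fisher's exact test with small cells covers only the other secondary outcomes.

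**The concern.** The upper confidence limit is the whole decision rule for this trial, so its construction and level should be fixed in advance. If they are not, the interval can be chosen after the counts are known.

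The construction that the text implies also has a known weakness here. The Wald standard error uses the observed proportions. When an arm happens to show few expulsions, the estimated difference is favourable and the standard error is small at the same time. The upper limit then falls below 6 points more often than its nominal level allows. About 6 expulsions are expected in the interval arm (4% of roughly 162), so the effect need not be negligible. It runs towards declaring early placement non-inferior when it is not. Section 9.4.2 itself foresees an arm with no or few expulsions, but only as an obstacle to imputation, and it gives no fallback for the primary test.

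**Working it through.** **Inputs.** From section 9.2: 202 per arm, interval-arm rate 4%, margin 6 points, 15% loss to follow-up, 5% not placed, two-sided alpha .05. From section 4.1: interval-arm range 3-5%. Assumption: the early-arm rate used for power is not stated and is taken as 4%, equal to the interval arm.

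**Evaluable women per arm.** 202 × 0.80 = 161.6 if the losses add; 202 × 0.85 × 0.95 = 163.1 if they multiply. The check uses 161, 162 and 163.

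**Reproducing the plan's 404.** With unpooled (Wald) variance, n per arm = (z_alpha + z_power)² × [2 × 0.04 × 0.96] / 0.06².

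- One-sided 2.5%: (1.960 + 0.842)² × 0.0768 / 0.0036 = 167.4, so 168. Then 168 × 1.20 = 201.6, so 202 per arm and 404 in total, which matches.
- One-sided 0.25%: (2.807 + 0.842)² × 0.0768 / 0.0036 ≈ 284 evaluable per arm, against about 162 planned. This does not match.

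The sample size therefore supports reading the rule as a two-sided 95% interval, one-sided error 2.5%.

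**False non-inferiority rate.** Let X be early and Y interval expulsions, independent binomials with n per arm, early rate = interval rate + 0.06. Sum the probability of every pair (X, Y) whose upper limit is below 0.06. The Wald upper limit is d + 1.96 × √[p1(1−p1)/n + p2(1−p2)/n], where p1 = X/n, p2 = Y/n and d = p1 − p2. The Newcombe upper limit is d + √[(u1−p1)² + (p2−l2)²], where u1 is the Wilson upper limit for the early arm and l2 the Wilson lower limit for the interval arm.

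| Interval rate | Wald, n = 161 / 162 / 163 | Newcombe, n = 161 / 162 / 163 |
|---|---|---|
| 3% | 3.58 / 3.58 / 3.47% | 2.36 / 2.32 / 2.25% |
| 4% | 3.24 / 3.39 / 3.29% | 2.34 / 2.38 / 2.31% |
| 5% | 3.03 / 3.20 / 3.11% | 2.31 / 2.46 / 2.40% |

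Miettinen-Nurminen gives 2.16-2.40% and Farrington-Manning 2.24-2.40% over the same nine cells.

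**Sensitivity.**

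- Equal arms of 155-170: Wald 2.92-3.64%, Newcombe 2.11-2.51%.
- Unequal arms (156 against 168, either way round): Wald 2.77-3.42%, Newcombe 2.25-2.41%.
- If the printed one-sided 0.25% were meant: Wald 0.41-0.62%, again above the stated rate, with exact power of only about 52% at 4% in both arms.
- If the interval-arm rate were below the documented range (an assumption), at 161 per arm: Wald 4.03% at a 2% rate and 4.90% at 1%.

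**A result that changes.** Take 8 early and 6 interval expulsions of 161 each: p1 = 4.97%, p2 = 3.73%, d = 1.24 points.

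- Wald: standard error √[(0.04722 + 0.03588)/161] = 2.27 points; upper limit 1.24 + 1.96 × 2.27 = 5.70 from unrounded values, so non-inferior.
- Newcombe: u1 = 9.50%, l2 = 1.72%; upper limit 1.24 + √(4.53² + 2.01²) = 6.20, so not shown.
- Farrington-Manning gives 6.25 and Miettinen-Nurminen 6.26, so not shown.

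The Wald and Newcombe conclusions also differ at 162 (5.66 against 6.16) and 163 (5.63 against 6.12).

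**Power, equal true rates in both arms, 161-163 per arm.**

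| Rate in both arms | Wald | Newcombe |
|---|---|---|
| 3% | 87.7-88.1% | 80.4-80.7% |
| 4% | 78.9-79.2% | 71.7-72.1% |
| 5% | 70.7-71.3% | 64.1-64.4% |

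**The case against.** Five points can be made for the plan.

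- **The 2.5% benchmark is inferred.** The figure is printed nowhere, and a Farrington-Manning sample size at one-sided 5% also lands near 404 (402-406). This stands as a caveat. The plan does print a two-sided .05, however, and Wald exceeds both printed alphas under the readings tested.
- **The method is not really missing.** A Wald test with an interval for the risk difference naturally means a Wald interval. That is fair, and it is the reading used here. The level is still absent from section 9.4.2, and section 9.2 gives conflicting rates from which to infer it.
- **The effect is small.** The excess is 0.5-1.1 points and is computed with the true difference exactly at the margin. There, Wald disagrees with Newcombe or Miettinen-Nurminen in 0.7-1.4% of trials. The Wald and Newcombe cut-offs usually differ by one early-arm event, and at 161 per arm they coincide for 5, 8, 10 or 11 interval expulsions. An Agresti-Caffo interval accepts 8 against 6 (upper limit 5.92), with an error of 2.60-2.95%. All of this stands and limits the weight of the point.
- **The remedy costs more than it gains.** The design appears to be sized on Wald variance, and a change of interval takes power at 4% from about 79% to about 72%; a score method reaches 80% only at about 202 evaluable per arm. The loss is real. Part of the Wald power, though, comes from exceeding the nominal error rate.
- **Both analyses may have to pass.** If the modified intention-to-treat and per-protocol analyses must both succeed, 3.0-3.6% is an upper bound. Section 9.4.2 does not say so.

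**Conclusion.** The concern holds. Section 9.4.2 leaves the level and construction of the deciding interval unstated, and the construction it implies does not hold the error rate implied by the two-sided .05. The excess is modest. It rests on these conditions: a two-sided 95% Wald interval, 161-163 evaluable per arm, interval-arm rates of 3-5%, an unstratified comparison, and the modified intention-to-treat analysis taken alone. The direction does not depend on the exact evaluable number, and the excess grows if expulsion is rarer than documented.

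Extending the fix to perforation is a matter of consistency and changes no decision. Section 2.3.1 reports no documented perforations in earlier early-placement studies. With 0 against 0 of 161, the Wald interval has zero width and the Newcombe upper limit is 2.3 points, and both lie below 6. This is something the sponsor should correct; it does not undermine the design.

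**What to change.** In section 9.4.2, replace the Wald test with wording such as:

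> Complete expulsion will be compared using a two-sided 95% Newcombe hybrid-score confidence interval for the risk difference (early minus interval). Non-inferiority is declared only if the upper limit is below 6 percentage points.

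Newcombe is suggested because, at 161-163 per arm, its error is as near or nearer to 2.5% than that of Miettinen-Nurminen, with no less power (71.7-72.1% against 69.8-71.8% at 4% in both arms). Miettinen-Nurminen is also acceptable if named in advance. The same interval should be used for the per-protocol set and for partial expulsion and perforation. Section 9.4.2 should also say whether both analysis sets must succeed.

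In section 9.2, reconcile the one-sided 0.25% with the two-sided .05, and restate the power for the chosen interval.

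The text change is one sentence in section 9.4.2 plus the corrected alpha and power in section 9.2, and the method is in standard software. The substantive cost is about 7 points of power at the planned rates, leaving about 72% against the stated 80%. The change does not itself require more enrolment, but the sponsor should report the lower power openly.

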9.4.3 ANALYSIS OF THE SECONDARY ENDPOINT(S)

Partial IUD expulsion and perforation will be analyzed with the same methods as the primary outcome. IUD discontinuation over the six-month study period will also be analyzed using survival analysis. Data will be censored either (1) at the last date of contact if a participant is lost to follow up or (2) time of IUD removal. The Log-rank test will be used for an unadjusted comparison of the two survival functions. This will be presented graphically using Kaplan-Meier curves.

For other secondary outcomes, normally distributed, continuous variables will be compared using Student's t-tests as appropriate. The Mann-Whitney U test will be used to compare other continuous variables that are not normally distributed. Proportions will be compared using chi-square tests. For small cell sizes, Fisher's exact test will be used as appropriate.

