1 PROTOCOL SUMMARY

1.1 SYNOPSIS

Title:	Early vs. Interval Postpartum IUD Insertion: A Multi-Site Randomized Controlled Non-Inferiority Trial
Study Description:	This is a randomized controlled non-inferiority trial comparing the expulsion rate of early postpartum IUDs (intrauterine devices) inserted between 2-4 weeks postpartum to the standard interval placement at 6-8 weeks postpartum
Objectives:	Primary Objective: Complete IUD expulsion at 6 months postpartum Secondary Objectives: Partial IUD expulsion at 6 months postpartum, IUD utilization, IUD removal, IUD perforation, pelvic infection, pain, vaginal bleeding, and user satisfaction at 6 months postpartum
Endpoints:	Primary Endpoint: Speculum and ultrasound evaluation Secondary Endpoints: Speculum, ultrasound and x-ray evaluation, self-reported outcomes (survey results)
Study Population:	Postpartum women who delivered an infant within the previous 10 days
Phase:	N/A
Description of Sites/Facilities Enrolling Participants:	Academic medical centers: the University of California, San Diego (UCSD); University of New Mexico (UNM); University of Illinois, Chicago (UIC); and Naval Medical Center, San Diego (NMCS)
Description of Study Intervention:	Postpartum insertion of IUDs at 2-4 weeks after delivery vs. 6-8 weeks after delivery
Study Duration:	2 years
Participant Duration:	6 months (with optional 12-month participation offered)

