3 OBJECTIVES AND ENDPOINTS

OBJECTIVES	ENDPOINTS	JUSTIFICATION FOR ENDPOINTS
Primary		
To determine if the risk of complete expulsion of EPP IUDs is non-inferior to interval PP IUDs	Diagnosis of IUD expulsion by speculum and ultrasound exam at 6 months postpartum. Expulsion defined as no IUD within the uterus by ultrasound or x-ray.	We propose that greater than or equal to a 6% difference in expulsion at 6 months postpartum between the two arms is clinically meaningful (6% non-inferiority margin).
Secondary		
To assess the proportion of participants utilizing the IUD at 6 months	Transvaginal and speculum exam to confirm presence of the IUD at 6 months.	From a public health perspective, the duration of IUD use is important for pregnancy prevention.
To determine if the risk of partial expulsion of EPP IUDs is non-inferior to interval PP IUDs	Diagnosis of IUD expulsion by speculum and ultrasound exam at 6 months postpartum. Partial expulsion defined as IUD protruding from the external cervical os on speculum exam or any part of the IUD seen below the internal cervical os on transvaginal ultrasound.	We propose that greater than or equal to a 6% difference in partial expulsion and perforation at 6 months postpartum between the two arms is clinically meaningful (6% non-inferiority margin).
Tertiary/Exploratory		
To assess the risk of perforation after EPP IUD compared to interval postpartum IUDs	IUD not visible in uterus on transvaginal ultrasound, but visible on pelvic x-ray at 6 months.	

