4.2 SCIENTIFIC RATIONALE FOR STUDY DESIGN

Traditionally, IUDs are placed at 6-8 weeks postpartum, therefore the standard of care will serve as the control condition. We are using a 6% non-inferiority assuming a 4% expulsions rate in the interval group according to prior research. This difference is presumed to be clinically meaningful.

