9 STATISTICAL CONSIDERATIONS

9.1 STATISTICAL HYPOTHESES

- Primary Efficacy Endpoint: Complete expulsion of IUDs placed in the early postpartum is non-inferior to IUDs placed at the standard interval time, assuming a 6% non-inferiority margin.
- Secondary Efficacy Endpoints:
 - The proportion of participants utilizing the IUD at 6 months postpartum will be greater in the EPP group compared to the interval group.
 - Partial expulsion of IUDs placed in the early postpartum is non-inferior to IUDs placed at the standard interval time, assuming a 6% non-inferiority margin.
 - There will not be a clinically or statistically significant difference in the proportion of participants diagnosed with a pelvic infection.
 - Proportion of participants agreeing or strongly agreeing that they are satisfied with the IUD, and the timing of IUD placement, will be similar between groups.

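### The 6-point expulsion margin and the Wald interval rule are also applied to uterine perforation, a rare event, with no rationale

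*Combined protocol and SAP*

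**What the plan says.** Section 9.4.3: "Partial IUD expulsion and perforation will be analyzed with the same methods as the primary outcome". Section 9.4.2 defines those methods as a Wald test with this decision rule: "If the CI for the risk difference does not cross the prespecified 6% margin, noninferiority will be confirmed". It gives no confidence level for the interval.

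The partial-expulsion row of the section 3 table extends the margin: "difference in partial expulsion and perforation at 6 months postpartum between the two arms is clinically meaningful (6% non-inferiority margin". The only quantitative basis for 6% is in section 4.2 (repeated in 9.2) and concerns expulsion: "We are using a 6% non-inferiority assuming a 4% expulsions rate in the interval group according to prior research".

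The status of perforation varies:
- The synopsis lists it among the secondary objectives: "IUD utilization, IUD removal, IUD perforation, pelvic infection, pain, vaginal bleeding, and user satisfaction at 6 months postpartum".
- Section 3 gives it a separate tertiary/exploratory row, with no margin and an empty justification cell: "To assess the risk of perforation after EPP IUD compared to interval postpartum IUDs".
- Section 9.1 has a non-inferiority hypothesis for partial expulsion ("Partial expulsion of IUDs placed in the early postpartum is non-inferior to IUDs placed at the standard interval time") but none for perforation.

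The Fisher's exact provision in 9.4.3 belongs to the paragraph on other secondary outcomes, so it does not replace the rule for perforation.

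**The concern.** A margin chosen for an event expected in about 4% of controls is very wide for an event the protocol treats as rare. Section 2.3.1 reports no documented perforations in over 200 early placements. The documents give no perforation rate for interval placement; section 2.2 mentions only a small increase in risk.

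The unpooled Wald interval also behaves badly at the counts expected here. It collapses to a point when both arms have no events, and its upper limit is too low when one arm has none.

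Section 2.3.1 names higher perforation with early placement as a possible risk, although it expects the opposite, and section 2.2 says the trial is meant to inform counselling on risks and benefits. A prespecified label of non-inferiority on a possible excess of a serious event, or an interval of zero width, would misinform that counselling.

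**Working it through.** **Inputs.** 202 per arm, 15% loss to follow-up, 5% not placed, 4% expulsion in controls, 80% power (9.2). Margin 6 points (3, 9.4.2). Section 9.2 gives two significance levels: two-sided .05, and "with a 1-sided type 1 error of 0.25" (percent). All true perforation rates below are assumptions.

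**1. The plan's own sample size.** n = 2 × 0.04 × 0.96 × (1.960 + 0.842)² / 0.06² = 167.4, so 168 per arm. 168 × 1.20 = 201.6, so 202 per arm and 404 in total, as stated. One-sided 0.0025 would need 285 per arm before inflation. The total therefore fits a 95% interval.

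**2. Evaluable number.** 202 × 0.80 = 161.6, taken as 161 (202 × 0.85 × 0.95 = 163.1; the same results pass or fail at 163). With 4% expulsion in both arms, SE = √(2 × 0.04 × 0.96 / 161) = 0.02184. Power is Φ(0.06/0.02184 − 1.960) = 78% at one-sided 0.025 and Φ(0.06/0.02184 − 2.807) = 48% at 0.0025. The first is close to the planned 80%.

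**3. The rule applied to perforation.** Wald interval: p₁ − p₀ ± z√(p₁q₁/n + p₀q₀/n). For 5 v 0, p₁ = 5/161 = 3.11% and SE = √(0.03106 × 0.96894 / 161) = 1.367 points, giving 3.11 ± 1.96 × 1.367. In the table, n = 161 per arm, early v interval, 95%, in percentage points:

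| Result | Wald | Rule | Miettinen-Nurminen | Fisher p |
|---|---|---|---|---|
| 0 v 0 | 0 to 0 | passes | -2.34 to 2.34 | – |
| 4 v 0 | 0.08 to 4.89 | passes | 0.12 to 6.22 | 0.12 |
| 5 v 0 | 0.43 to 5.79 | passes | 0.73 to 7.07 | 0.061 |
| 6 v 0 | 0.80 to 6.65 | fails | not computed | 0.030 |

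Over all possible results, only 4 v 0 and 5 v 0 both pass and lie wholly above zero on the Wald interval. With the score interval both miss the 6-point margin, so the label depends on the interval method.

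**4. Sensitivity.** At 150 per arm and 95%, 5 v 0 fails (0.46 to 6.21), and only 4 v 0 both passes and excludes zero (0.09 to 5.24). At 161 and 99.5%, 4 v 0 passes but includes zero (-0.96 to 5.93), 5 v 0 fails (-0.73 to 6.94), and no result does both. The zero width at 0 v 0 occurs at every n and level.

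**5. How often the rule passes** (exact binomial, 161 per arm, 95%):

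| True early rate | Declared non-inferior, control 0.5% | 4 v 0 or 5 v 0, control 0.1% / 0.5% / 1% |
|---|---|---|
| 1% | 99.5% | 6% / 3% / 1.5% |
| 2% | 91% | 25% / 13% / 6% |
| 3% | 67.5% | 31% / 16% / 7% |

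These are not error rates, since every true difference here is below 6 points. They show how wide 6 points is for a rare event.

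**6. Chance of no events.** P(0 v 0) = (1 − p)^322, which is 72%, 45% and 20% if both true rates are 0.1%, 0.25% and 0.5%. The exact upper 95% limit for 0/161 is 1 − 0.025^(1/161) = 2.3%.

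**The case against.** The strongest reply is that no non-inferiority claim on perforation was intended. Perforation's own row is exploratory and has no margin, 9.1 has no such hypothesis, and the margin reaches perforation through two words in another row. That may explain how the text arose, but the margin is printed and 9.4.3 applies the primary methods without limit, so the passages need reconciling on either reading.

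Section 3 does call 6% clinically meaningful for perforation. That is an assertion without reasoning.

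The 5 v 0 example is fragile, and this stands. It needs about 161 per arm and a 95% interval, it fails at 155 per arm (upper limit 6.01), and Fisher's test does not establish an excess. Early rates of 2% or 3% are also above what 0 in 200 suggests (exact upper limit 1 − 0.025^(1/200) = 1.8%), though completeness of follow-up in those studies is not given. The 0 v 0 case does not depend on these conditions.

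Safety review is separate. The table of serious events (9.4.4) and the triggers for convening the data safety and monitoring board (8.2), including more than four related serious events or a rate above 1%, mean the events would be seen. Five perforations among 404 women is 1.2%. Review does not change the prespecified label, so the same 5 v 0 could trigger a board review and be reported as non-inferior.

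**Conclusion.** The concern holds. As written, the plan judges perforation by a margin justified only for expulsion and by an interval unsuited to sparse counts. The more likely failure is the zero-width interval at 0 v 0, which needs no assumption about sample size or confidence level; how often it would occur (20% to 72%) rests on assumed rates. The second failure, 4 v 0 or 5 v 0 labelled non-inferior with the interval above zero, rests on 161 evaluable per arm and a 95% level. It shows a possible excess, not a proven one. The effect is confined to how a secondary or exploratory safety outcome is reported. The plan should be corrected, but the primary conclusion does not depend on it.

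**What to change.** In section 3, remove perforation from the 6% margin text. Give perforation the same status in the synopsis and section 3. In 9.4.3, limit the primary-outcome methods to partial expulsion and add:

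> Perforation will be reported descriptively: counts by arm, an exact 95% confidence interval for each rate, and a score-type (for example Miettinen-Nurminen) 95% interval for the risk difference. No non-inferiority conclusion will be drawn.

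A smaller perforation-specific margin is possible but would need its own justification and has limited power here. With the score interval at 161 per arm, a 2-point margin is missed even at 0 v 0 (upper limit 2.34). A 3-point margin passes at 0 v 0 and 1 v 1 (2.87) but not at 1 v 0 (3.44); its power is 65%, 76% and 87% if both true rates are 0.5%, 0.25% and 0.1%.

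The cost is wording in three places, with no new data or participants. The trial gives up a perforation non-inferiority claim that 9.1 does not list.

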8 STUDY ASSESSMENTS AND PROCEDURES

8.1 EFFICACY ASSESSMENTS

a. Admission/Enrollment Procedure

All women in the 4 study health centers are educated about postpartum contraception during antenatal care. All postpartum women who do not receive an IPP IUD or tubal ligation will be asked if they are interested in the IUD for contraception while on the postpartum floor. If they plan to choose an IUD they will be asked for verbal assent to be pre-screened for the study. If a woman gives verbal consent to be pre-screened, a research assistant will administer the Pre-Participation Questionnaire/Eligibility Checklist. Women who meet inclusion criteria, meet no exclusionary criteria, and want to participate, will be formally consented to participate in the study. Signed informed consent forms will be collected. Subjects will be given copies of the consent document and a copy of the "Experimental Subject's Bill of Rights," and a HIPAA Authorization form for medical data to be released for research purposes. Enrolled participants will then be randomized to EPP or Interval PP IUD placement within 10 days of delivery. The Research Assistant (RA) will open the sealed envelope with the appropriate randomization envelope for the assigned participant number to unblind the participant to her assigned group. Participant numbers are assigned sequentially by each site. Participants will then be asked to complete the Baseline questionnaire.

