9.3 POPULATIONS FOR ANALYSES

The following datasets will be utilized for analysis:

- Intention-to-Treat Analysis Dataset: All participants randomized with known outcomes at the 6 month follow up visit*.
- Modified Intention-to-Treat Analysis Dataset: Participants who received an IUD within 6 months of delivery with known outcomes at the 6 month follow up visit*.
- Per-Protocol Analysis Dataset: Participants who received an IUD within the specified timeframe as designated by their group assignment with known outcomes at the 6 month follow up visit (14-28 days in the early group and 42-56 days in the interval group)*.

*participants known to have an IUD outcome by ultrasonography, pelvic examination, or a contact up to 240 days postpartum will be included.

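### Section 9.4.3 states no time zero for the IUD discontinuation analysis; on an enrollment or delivery clock the log-rank test is shifted against early placement

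*Combined protocol and SAP*

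**What the plan says.** Section 9.4.3 plans that "IUD discontinuation over the six-month study period will also be analyzed using survival analysis". It adds that "The Log-rank test will be used for an unadjusted comparison of the two survival functions" and that Kaplan-Meier curves will be shown. Removal is one of its two censoring reasons: "Data will be censored either (1) at the last date of contact if a participant is lost to follow up or (2) time of IUD" (the sentence ends by naming removal). It gives no time zero, no analysis set for this endpoint and no definition of the event.

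Other sections bear on the clock:

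- Section 4.1 describes a trial that "includes 6 months of participation from enrollment to final follow-up".
- Section 8.1 sets the time of allocation: "Enrolled participants will then be randomized to EPP or Interval PP IUD placement within 10 days of delivery". Allocation therefore precedes insertion in both arms.
- Section 4.3 places the last required visit at 6 months postpartum for everyone.
- Section 9.3 gives the insertion windows as "14-28 days in the early group and 42-56 days in the interval group", counted from delivery.

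**The concern.** A woman cannot discontinue an IUD that she does not yet have. On a clock that starts at enrollment or delivery, every woman passes through a stretch in which an event is impossible, and the assigned timing makes that stretch about four weeks longer in the interval arm. Randomization does not remove the difference, because the allocation creates it. Restricting the analysis to women who received an IUD does not remove it either, since the wait before insertion stays in the risk set.

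The log-rank test and the curves would then tend to show more discontinuation with early placement when the two timings perform identically after insertion. Section 2.2 says the trial is meant to support counseling on early placement, and the synopsis lists IUD removal among the secondary objectives. A gap produced by the clock could be read as poorer retention of early IUDs. With the origin unstated, it could also be chosen after the data are seen.

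**Working it through.** The plan gives no rate, effect size or power for discontinuation, so there is no figure of its own to reproduce. The check has three steps.

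**1. Which clock the text suggests.** Take 6 months as day 182 and insertion at the window midpoints: day 21 = (14 + 28)/2 for early and day 49 = (42 + 56)/2 for interval.

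- Time from insertion to the visit: 182 − 21 = 161 days (early) and 182 − 49 = 133 days (interval). Neither is six months.
- An enrollment or delivery clock fits a six-month period in both arms to within the 10 days allowed before randomization.

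The wording therefore points to enrollment or delivery, but it fixes a window and not an origin.

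**2. Exposure and expected proportions.** The gap between windows is 42 − 14 = 49 − 21 = 56 − 28 = 28 days. An enrollment origin moves both arms by the same amount and leaves the gap unchanged. The exposure ratio is 161/133 = 1.21.

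Let p be the assumed early-arm proportion discontinued by day 182. With the same constant hazard after insertion in both arms:

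h = −ln(1 − p)/161, and interval-arm proportion = 1 − exp(−133h) = 1 − (1 − p)^(133/161)

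For p = 10%: 1 − 0.90^0.826 = 8.3%, an apparent excess of 1.7 points with no true difference.

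**3. Effect on the log-rank test.** Simulation inputs:

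- 162 women per arm: 202 × (1 − 0.15 − 0.05) = 161.6, from section 9.2;
- insertion uniform within each window, and follow-up to day 182;
- the same discontinuation hazard by time since insertion in both arms, either constant or front-loaded (Weibull shape 0.5);
- all discontinuations counted as events;
- 1,000 runs per scenario.

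The last two columns show how often the test found early placement significantly worse on a delivery clock (nominal 2.5%).

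| Assumed p, early | Interval, constant hazard | Apparent excess | Early found worse, constant | Early found worse, front-loaded |
|---|---|---|---|---|
| 5% | 4.1% | 0.9 points | 4.9% | 3.9% |
| 10% | 8.3% | 1.7 points | 8.5% | 4.1% |
| 15% | 12.6% | 2.4 points | 10.4% | 5.0% |
| 20% | 16.8% | 3.2 points | 11.6% | 7.3% |

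Mean Z on the delivery clock was 0.36 to 0.85 (constant) and 0.19 to 0.54 (front-loaded), always against early placement. The front-loaded shift is smaller because interval-arm women are in their higher-risk early weeks of use after day 42, which partly offsets the gap. Simulation error reaches about 1 point: √(0.116 × 0.884/1000) = 0.010. A separate run over assumed rates of 4-20% gave mean Z of 0.20 to 0.76 and early found worse in 3.4-11.9% of trials.

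With time zero at insertion, mean Z was −0.08 to +0.04 and two-sided rejection was 3.5-5.4% (nominal 5%). The shift is gone.

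**The case against.** **The plan does not say that it uses an enrollment clock.** A reader might infer from section 4.1 that it does. That sentence describes how long a woman takes part, not a survival origin. Discontinuation presupposes a device, and nothing in the plan rules out time from insertion. This stands: the bias is conditional on the clock.

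**Four weeks is a difference between arms.** A reader might take it as the interval arm's whole wait. From delivery, that wait is 6-8 weeks, and early-arm women wait 2-4 weeks.

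**This is not the usual immortal-time error.** Arm is fixed by randomization before any insertion, so no time is credited to the wrong group. A comparison on postpartum time of two placement strategies is a legitimate question, and the trial asks it for expulsion and for use at 6 months. This also stands. But section 9.4.3 does not say that it wants the strategy question here, and use at 6 months already answers it. A curve labeled as discontinuation will be read as retention after placement.

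**Read literally, the plan censors removals.** Events would then be mainly expulsions. At an assumed 4% over 180 days, a simulation of 2,000 runs gave two-sided rejection of 5.6% (constant hazard) and 4.9% (front-loaded, shape 0.6), with excesses of 0.6 and 0.4 points. On that reading the clock hardly matters, but the analysis would no longer measure discontinuation. Both points need correcting together.

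**The analysis is minor.** It is not among the section 3 objectives or the section 9.1 hypotheses, and it carries no margin or power claim. This limits the consequence but does not remove the reason to state the clock.

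**Conclusion.** The point holds conditionally. Time zero is not defined, and the wording leans toward enrollment or delivery. On either clock, interval-arm women carry about 28 more days without an IUD in the risk set, and the log-rank test is shifted against early placement. For assumed discontinuation of 4-20%, early is wrongly found worse in roughly 3-12% of trials against 2.5% nominal. The apparent excess is about 1 to 3 points at 5-20% under a constant hazard. At the low end, or with front-loaded discontinuation, the distortion is small.

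These figures rest on assumed rates, insertion inside the windows, about 162 evaluable women per arm, and removals counted as events. The modified intention-to-treat set admits insertion at any time within 6 months of delivery, so the real gap will depend on actual insertion dates.

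A reader might infer that the trial's main conclusion is at risk. The documents do not support that: the primary endpoint is a proportion at 6 months with its own margin and does not use this clock.

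**What to change.** In section 9.4.3:

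- Define time zero as the date of IUD insertion, among women who received an IUD.
- Count removal and expulsion as events, and delete removal from the censoring reasons. Without this, the change of clock does not give a discontinuation analysis.
- Say how an expulsion first found at the 6-month visit is dated.
- Censor at the last date of known IUD status, up to the 6-month assessment.
- Show the curves only over the time since insertion that both arms cover. For insertion at the end of the interval window this is 182 − 56 = 126 days, or 18 weeks.
- If a postpartum time scale is also wanted, enter each woman at her insertion date (delayed entry). This removes the device-free time, but it compares women at different durations of use, so it should supplement the insertion clock and not replace it.

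The cost is a few sentences. Insertion dates are already needed for the per-protocol set, and removal dates for the censoring rule as written. No extra participants are needed.

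There are two drawbacks. The comparison becomes conditional on receiving an IUD, as the modified intention-to-treat set already is. Follow-up since insertion is also about four weeks shorter in the interval arm. The proportion using an IUD at 6 months postpartum remains the comparison of the two strategies.
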